7.4.2 Suspected Unexpected Serious Adverse Reactions (SUSARs)

For SUSARs, the PI or co-investigator(s) will need to complete additional SUSAR related questions within the SAE

These questions constitute the SUSAR eCRF, which must be signed electronically within the web application by the PI or delegate within 24 hours of becoming aware of the event. If for any reason the web application cannot be accessed, a paper SUSAR CRF should be completed and faxed to the number above in section 7.4.1.

The Barts CTU will inform the CI (or delegate), and sponsor immediately so that they can review the information jointly and report to the MHRA within the allocated timelines.

The sponsor has a legal obligation to report SUSARs to the MHRA within 7 days (for fatal or life threatening SUSARs), or 15 days for all other SUSARs. Barts CTU will notify the REC of any SUSARs within the same timeframes. Barts CTU will also inform the IMP supplier within the timescale agreed.

All participating sites will be informed of SUSARs that occur during the trial by the Barts CTU, as and when they occur. If warranted, an investigator alert may be issued, to inform all investigators involved in any study using the same drugs that this serious adverse event has been reported.

The original and any subsequent follow up of SUSAR eCRFs must be electronically signed by the PI or delegate, within the PROVENT web based application, and the form/s must be emailed to the sponsor. A copy of the form(s), together with the email confirmation of receipt, from the Sponsor, must be kept within the TMF. The local sites should keep all SUSAR CRFs within their IF.

7.5 Urgent Safety Measures

The CI may take urgent safety measures (USM) to ensure the safety and protection of the clinical trial subjects from any immediate hazard to their health and safety, in accordance with Regulation 30 of the Medicines for Human Use (Clinical Trials) Regulations 2004. The measures should be taken immediately. In this instance, the authorisation of the Licensing Authority Approval prior to implementing these safety measures is not required. However, The CI will make every effort to discuss the USM with the Sponsor and if possible the MHRA via telephone prior to implementation.

It is the responsibility of the CI to inform both the MHRA and REC immediately and in writing within 3 days, in the form of a substantial amendment. A copy of the correspondence with regards to this matter will be sent to the sponsor and the IMP supplier.

7.6 Annual Safety Reporting

The Development Safety Update Report (DSUR) will be sent to the REC, MHRA and IMP suppliers by the CI or delegate, following the sponsor's review, using the DSUR form. The date of the anniversary is the date on the 'notice of acceptance letter' from the MHRA. The CI will carry out a risk benefit analysis of the IMPs encompassing all events having arisen on the trial.

The CI will send the Annual Progress Report to the main REC, following review by the sponsor, using the HRA template (the anniversary date is the date on the 'favourable opinion' letter issued by the REC).

7.7 Procedures for Reporting Blinded SUSARs

The responsibility for Pharmacovigilance management and reporting is allocated to the CI by the sponsor. Under these circumstances, a dedicated individual(s), with no involvement in data management of the study will be responsible for the un-blinding event. The un-blinding of single cases by the PI/CI in the course of this study will only be performed if necessary for the safety of the trial subject, or if the participant expresses an explicit wish to know the treatment he is or was receiving. See section 5.10.

Any occurrences will be assessed for seriousness, expectedness and causal relationship as if it was the tested IMP that caused the reaction. If the case appears to be a SUSAR it will be un-blinded to the Sponsor and, if the administered product is the tested IMP, the case will be reported by the sponsor as a SUSAR to the MHRA, the Main Research Ethics Committee and the IMP provider by Barts CTU within the timelines outlined in section 7.4.2. The blind will be maintained for the study team, excluding staff involved in data analysis & interpretation,

7.8 Overview of the Safety Reporting Process/Pharmacovigilance Responsibilities

The CI has the overall pharmacovigilance responsibility. The CI has a duty to ensure that Pharmacovigilance monitoring and reporting is conducted in accordance with the sponsor's requirements.

8.0 Statistical Considerations

8.1 Primary Endpoint Efficacy Analysis

The primary endpoint of the study is the rate of patient recruitment. This will be captured by reporting the proportion of eligible patients that join the trial over the 12-month trial recruitment period.

After a recruitment period of 9 months, the Data Monitoring Committee will identify whether study recruitment has been adequate, i.e. an average recruitment rate of 6 patients per month, and if monitoring of 50% of the feasibility group shows minimal adverse effects in any arm of the trial, this information will be used to justify the main trial.

8.2 Secondary Endpoint Efficacy Analysis

The secondary endpoints include response to treatment as determined by serial multi-parametric magnetic resonance imaging (MRI) of the prostate, biochemical disease progression, histological disease progression together with the evaluation of markers of disease progression.

- Disease progression on MRI will be defined as the development of a MRI detected lesion of 0.2 cc or greater and scoring 4/5 on PIRADS criteria, where no MRI lesion was identified on screening MRI, a 33% increase in the volume of previously identified lesions or an upgrading of MRI stage of disease to ≥3.
- . The outcome will be described as a proportion of the study cohort.

Biochemical disease progression will be defined as a 50% increase in serum PSA at 12 months from baseline. Again this will be described as a proportion of the study cohort.

Histological disease progression will be defined as an increase in Gleason score following repeat prostate biopsy from:

Gleason 6 to Gleason score 7 or higher Gleason 3+4 (score 7) to 4 + 3 (score 7) or Gleason 4+3 (score 7) to a higher score

Or a 50% increase in maximum cancer core length (MCCL)

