Depending upon the criteria used to define prostate cancer progression; 30-50% of men entered into an Active Surveillance programme are identified as experiencing disease progression and subsequently undergo radical therapy[8, 9]. A high proportion of men are therefore still experiencing the harms associated with prostate cancer therapy. It would therefore be highly advantageous to identify an agent that would be able to reduce the number of men experiencing disease progression while enrolled in an Active Surveillance programme.

The purpose of this study is to test the feasibility of recruiting to the larger randomised trial that would assess the efficacy of both aspirin and/or Vitamin D3 to prevent prostate cancer progression in men entered into an Active Surveillance programme.

Criteria for Active Surveillance

A number of different criteria exist for Active Surveillance[8]. The criteria for surveillance are often based on a combination of factors including serum PSA, PSA density together with histological biopsy findings (including the number of positive prostate cancer cores), the percentage of positive cancer cores to negative cancer cores, and the grade of the cancer on prostate biopsy.

Criteria for cancer progression

Again, criteria for disease progression are numerous. Many have used PSA velocity while on surveillance, although increasing data suggest that PSA dynamics on surveillance do not correlate with adverse findings on repeat prostate biopsy. Such adverse features correspond to more extensive disease on repeat biopsy together with higher grade disease on repeat biopsy. Generally, if a man transitions from what is regarded as lower risk disease to clinically significant disease, many clinicians would recommend he undergoes radical therapy.

The criteria for cancer progression for this study will be based on any of the following:

- the development of a minimum 0.2cc lesion, with a PIRADS score of 4/5, on multi-parametric imaging where no MRI lesion was identified at the screening MRI, or an MRI scan demonstrates that a lesion identified at screening has increased in volume by >33%
- An upgrading of MRI stage of disease to ≥T3.
- A 50% increase in serum PSA at 12 months from baseline.
- Histological disease progression defined as an increase in Gleason scores from:

Gleason 3+3 to Gleason score 7 or higher Gleason 3+4 (score 7) to 4+3 (score 7) or Gleason 4+3 to a higher score

- A 50% increase in maximum cancer core length (MCCL)

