2.2 Secondary Objectives and Endpoints

Objectives	Endpoints	Assessment Method
To report response to treatment as determined by serial multiparametric magnetic resonance imaging (MRI) of the prostate.	The development of a lesion on multi-parametric imaging where no MRI lesion was identified on screening MRI, an MRI scan that demonstrates that a lesion identified on the screening MRI has increased or decreased in volume by greater than 33%, or an upgrading of MRI stage of disease to ≥T3. 50% increase in serum PSA at 12 months from baseline	Results collected on Case Report Forms (CRFs) after MRI scanning
To report biochemical disease progression	Histological disease progression will be defined as an increase in Gleason	Routine 3-monthly blood samples
To report histological disease progression	scores from: Gleason 3+3 to Gleason score 7 or higher Gleason 3+4 (score 7) to 4+3 (score 7) or Gleason 4+3 to a higher score Or a 50% increase in maximum cancer core length (MCCL)	Routine 12-month biopsy
To assess consistency in local reporting and establish the necessity for central review of the pathology reports, in the main		Central review of at least 10% of all prostate biopsy tissue
trial. To report toxicity and/or allergy to both aspirin and Vitamin D3	Aspirin toxicity: Haemorrhagic stroke, anaphylaxis following administration, gastrointestinal bleeding requiring intervention (both medical and surgical) Vitamin D3 toxicity: Hypercalcaemia, Anaphylaxis	Adverse events recorded on the CRF 3-monthly up to month 15 th , and then for a further 4mths.
To evaluate an association between androgens and disease progression		Blood sample for serum Vitamin D3 and corrected calcium levels 6 monthly

To evaluate markers of disease progression

Cell Cycle Progression (CCP(ii)) scores

Cell Cycle Progression (CCP(ii)) scores

Urine sample and testing at Molecular Epidemiology Laboratory, QMUL

See Section 5.7 for details of laboratory assessments

Prostate biopsy tissue testing by Myriad Genetics

MRI imaging will be reported according to local practice. Lesion volumes will be measured by planimetry on all sequences. Diffusion and/or dynamic contrast enhancement sequences will be included in this assessment [43]. Scans will be reviewed locally by a specialist radiologist, and the baseline and subsequent scan directly and concurrently compared.

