5.8 Radiology Assessments

Patients will undergo Magnetic Resonance Imaging (MRI) prior to entry and at 12 months as part of their routine treatment on Active Surveillance.

Progression of prostate cancer will be defined as the development of a lesion on multi-parametric imaging where no MRI lesion was identified on the screening MRI, or alternatively, an MRI scan that demonstrates that a lesion identified on screening MRI has increased in volume over the study period by greater than 33%.

Patients will undergo multi-parametric MRI imaging of the prostate. The scan will be performed & reported using each site's routine practice and locally defined parameters. The details of the procedure & the results will be recorded on a 'MRI Procedure & Results' eCRF. In addition, a pseudo-anonymised copy of the report will be uploaded to the PROVENT application.

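### As worded, a new MRI lesion counts as MRI progression only in men with a clear screening scan, so a separate new lesion in a man who already had one meets no MRI criterion

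*Protocol*

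**What the plan says.** Section 8.2 defines MRI progression by three routes. The first is a new lesion of at least 0.2 cc that scores PIRADS 4/5, but only "where no MRI lesion was identified on screening MRI". The second and third routes are "a 33% increase in the volume of previously identified lesions or an upgrading of MRI stage of disease to ≥3". The result is to be described as a proportion of the whole study cohort.

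The same condition on the new-lesion route appears in three other places:

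- Section 1.1 (criteria for cancer progression) counts a new lesion "where no MRI lesion was identified at the screening MRI, or an MRI scan demonstrates that a lesion identified at screening has increased"; the growth has to exceed 33%.
- Section 2.2 (secondary endpoint table) has "The development of a lesion on multi-parametric imaging where no MRI lesion was identified on screening MRI".
- Section 5.8 has "the development of a lesion on multi-parametric imaging where no MRI lesion was identified on the screening MRI, or alternatively" growth of a screening lesion.

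Section 3.2 admits men whose screening MRI shows a lesion, provided that the lesion and the positive biopsy core agree in location. It does not say how many such men are expected.

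**The concern.** The new-lesion route depends on the man's whole screening scan, not on the place where the new lesion appears. Two men can develop the same lesion at 12 months and be scored differently. The man whose screening scan was clear has progressed on MRI. The man who already had a small, stable lesion elsewhere in the gland has not.

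This affects how the endpoint can be read. Men with a screening lesion can lose an event but remain in the denominator, so the pooled proportion mixes two definitions. The MRI objective is the first listed among the secondary objectives, and its result would be hard to interpret or carry forward to a larger trial.

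**Working it through.** The protocol states no figure for the MRI progression proportion, so there is nothing to reproduce. The check sets the four definitions side by side.

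| Section | New lesion requires a clear screening scan | 0.2 cc and PIRADS 4/5 threshold | Growth of a known lesion | MRI stage upgrade |
|---|---|---|---|---|
| 1.1 | yes | yes | more than 33% | yes |
| 2.2 | yes | no | more than 33% (a decrease is also listed) | yes |
| 5.8 | yes | no | more than 33% | not listed |
| 8.2 | yes | yes | 33% | yes |

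**Test case.** Take a man with one lesion at screening. At 12 months that lesion is unchanged, his stage is unchanged, and a separate lesion of at least 0.2 cc scoring PIRADS 4/5 has appeared.

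1. New-lesion route: not met in any of the four sections, because his screening scan showed a lesion.
2. Growth route: not met, because the known lesion is stable.
3. Stage route, where listed: not met.

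He is scored as having no MRI progression. He is eligible under section 3.2 and counted in the denominator under section 8.2.

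**Size.** The number of men affected is

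N × L × q,

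where N = 102 (section 3.1), L is the share with a screening lesion, and q is the share of those who develop a separate qualifying lesion without index growth or upstaging. The protocol gives neither L nor q. The ranges below are assumptions for illustration.

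| L | q | Men affected | Percentage points of the cohort |
|---|---|---|---|
| 40% | 5% | 102 × 0.40 × 0.05 = 2.0 | 2.0 |
| 40% | 15% | 102 × 0.40 × 0.15 = 6.1 | 6.0 |
| 70% | 5% | 102 × 0.70 × 0.05 = 3.6 | 3.5 |
| 70% | 15% | 102 × 0.70 × 0.15 = 10.7 | 10.5 |

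The range is about 2 to 11 men.

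**The case against.** **The word 'where' may refer to a site.** It can be read as 'at a site where', which would count a second lesion. Section 8.2 speaks of previously identified lesions in the plural, which is lesion-level language, and section 2.2 has the baseline and later scans compared directly. This reading is possible. But no section names a site, and sections 1.1 and 5.8 set the condition against growth of a lesion seen at screening, which sorts men by baseline status. What stands of the objection is that the rule may be ambiguous rather than plainly wrong. As scans are reported by local practice at up to seven centres, ambiguity alone is reason to settle the wording.

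**Such men may be caught elsewhere.** Section 1.1 counts progression on any one criterion, and section 5.4 has MRI abnormalities targeted at the 12-month biopsy. A man missed on MRI may therefore count overall through Gleason score, core length, PSA or metastases. This stands: the loss is certain only for the MRI endpoint.

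**The analysis plan or the case report form may settle it.** They may add detail, but the protocol itself fixes the rule in four places, so the point concerns what is stated, not what is left out.

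**The endpoint is minor.** It is a secondary, descriptive endpoint in a study whose primary endpoint is recruitment, and no stated figure changes. This stands and limits the weight of the point.

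**Conclusion.** The point holds for the MRI endpoint. On the plain reading of 8.2, 2.2 and 5.8, a separate new lesion in a man with a stable screening lesion and unchanged stage is not MRI progression; on the most generous reading, the text leaves it to each reader. The size cannot be derived from the protocol, and the 2 to 11 men rest wholly on the assumed shares. It is a small improvement to make, not a threat to the study's main aim.

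Three stronger conclusions that a reader might draw are not supported:

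- *That the rule distorts comparisons between arms of 17.* Section 8.2 plans a cohort proportion and specifies no arm comparison of MRI progression. The comparisons in section 8.5 concern assays, for each drug against its placebo. On planned numbers those margins are 3 × 17 = 51 against 51 for Vitamin D3 and 2 × 17 = 34 per aspirin level.
- *That 2 to 11 men should be set against about 31 progressors (102 × 0.30 = 30.6).* The 30% in section 3.4 is an upper figure for overall reclassification by MRI and biopsy together, not for MRI alone, and some of the affected men may be among those 31.
- *That the sizing of the definitive trial is compromised.* Section 1.5 ties that to histological or biological progression, so the part played by MRI is unclear.

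**What to change.** In the endpoint definition in section 8.2, change the condition to *at a site where no lesion was identified on the screening MRI*, so that it applies to every man. Carry the same site wording to the endpoint text in 2.2 and 5.8. Report MRI progression also by baseline lesion status.

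Two matters are for the sponsor to reconcile:

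- The 0.2 cc and PIRADS 4/5 threshold stands in 1.1 and 8.2 but not in 2.2 and 5.8. It should be settled openly in the same edit, not altered as a side effect.
- Section 1.1 also serves sections 3.4 and 5.6, which deal with continuing on or leaving the study. Its relation to the endpoint definition needs to be made explicit. No clinical rule is proposed here.

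The cost is small. The endpoint change is one phrase, and because baseline and later scans are already to be compared directly, it needs no new scan or procedure. The downside is a slightly higher MRI progression proportion.

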	 Gleason score 6 or 7 (Gleason 3+3 or 3+4) Clinical and radiological stage <t3< li=""> Serum PSA ≤15.0 ng/ml Less than 10mm of cancer in a single core </t3<>
	Previously treated prostate cancer (including radiotherapy, hormone therapy, brachytherapy or surgery)
	 Currently enrolled, or has been a participant within the last 30 days, in any other investigational drug or device study. Current daily use of aspirin or NSAIDs; or daily dietary supplements/medication containing more than 400 IU (10 micrograms per day) Vitamin D3; or chronic use (defined as > 6 months continuous daily use) of either aspirin or >400IU Vitamin D3 within two years of study enrolment
	4. Current or previous use of 5- α reductase inhibitors such as finasteride or dutasteride
	 Not willing to comply with the procedural requirements of this protocol including repeat prostate biopsies
	 Known allergy/sensitivity to or intolerance of aspirin, other salicylates or NSAIDs e.g. ibuprofen/ naproxen
Exclusion Criteria	 Prior history of gastro-intestinal bleeding or ulceration, severe dyspepsia or inflammatory bowel disease
	8. Haemophilia or other bleeding diatheses
	9. Prior history of renal stone disease
	10. Chronic renal disease (≥stage 4)
	 Known hypercalcaemia (corrected serum calcium >2.65 mmol/l) or untreated hyperparathyroidism
	12. Any bowel condition that would make repeat transrectal biopsy hazardous or difficult to perform e.g. recto-urethral fistula, or prior bowel surgery such as abdomino-perineal resection.
	13. Any malignancy (other than non-melanoma skin cancer) that has not been in complete remission for five years

	Any serious co-existent medical condition that would make repeat prostate biopsy hazardous e.g. anti-coagulation requiring continuous administration
	15. Severe Asthma
	16. G6PD deficiency
	17. Pre-existing macular degeneration
	18. All contraindications to aspirin and Vitamin D3, including concomitant therapy with any medication that may interact with aspirin or Vitamin D3 (see section 4.10)
	19. Regular consumption of alcohol units greater than the recommended daily limit of 3-4 units per day (men)
	Sample size calculations have suggested that 800 men are needed for a future definitive randomised chemoprevention study of standard (300mg) or low dose (100mg) aspirin vs. placebo and/or Vitamin D3 vs. placebo in patients enrolled on an Active Surveillance programme for prostate cancer.

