3.2 Inclusion Criteria

- 1. Male subjects aged 16 years or over with an estimated life expectancy of more than 3 years
- 2. Willing and able to provide written informed consent
- 3. Serum calcium (corrected) ≤2.65mmol/l
- 4. No previous treatment for prostate cancer (including surgery, hormone therapy, radiotherapy, cryotherapy)
- 5. All subjects must have undergone Magnetic Resonance Imaging (MRI) of the prostate with targeted biopsy of any identified lesions in addition to standard systematic biopsy.
- 6. Histologically confirmed prostate cancer following prostate biopsy including at least 10 cores of prostate tissue, in men opting for Active Surveillance as their primary cancer therapy.

Biopsies should be at least a 10-core systematic ultrasound guided prostate biopsy. For the majority of men the route of biopsy is likely to be transrectal, although the perineal route is not a contraindication to study participation. Targeted biopsies may be performed via the transrectal or perineal route. Men are eligible for the PROVENT study providing concordance exists between the location of MRI detected lesion and the location of positive biopsy core. If no concordance exists, a further prostate biopsy with lesion targeting will be required prior to randomisation, and histological analysis must fulfil study definition as a low to intermediate risk prostate cancer.

Targeted biopsies of MRI lesions must be sent in a separate pot/s from systematic biopsies and be clearly labelled. A minimum of two targeted biopsies per MRI detected lesion is required.

At 12 months, all men will be required to undergo repeat prostate biopsy. Again, the route of biopsy, transrectal or perineal, is not mandated. Patients must have systematic and targeted biopsies at the 12-month point using the same methods as described at study entry.

All patients included in the study should be enrolled in an Active Surveillance management programme for prostate cancer. Patients may be included if they have Gleason 6 or 7, (Gleason 3+3 or 3+4), organ confined disease, with a PSA of 15.0 ng/ml or less, and have a clinical and radiological stage of less than T3. The largest cancer core length should be less than 10mm.

Patients must have undergone a multi-parametric MRI deemed assessable by the study radiologist, and any lesions seen must have undergone targeted biopsy (transrectal or transperineal) within 12 months of study registration.

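### The histological progression list omits a rise from Gleason 3+4 to score 8 or more, and its 4+3 starting row fits no eligible baseline grade

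*Protocol*

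**What the plan says.** Section 8.2 opens the definition with "Histological disease progression will be defined as an increase in Gleason score following repeat prostate biopsy from" and then lists the transitions. The first runs from Gleason 6 to score 7 or higher. The rest is "Gleason 3+4 (score 7) to 4 + 3 (score 7) or Gleason 4+3 (score 7) to a higher score". The only alternative route to histological progression is "Or a 50% increase in maximum cancer core length (MCCL").

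Sections 1.1 (criteria for cancer progression) and 2.2 (secondary endpoints) repeat the list, with the first row written as 3+3 and the others as "Gleason 3+4 (score 7) to 4+3 (score 7) or Gleason 4+3 to a higher score".

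On entry, section 3.2 says "Patients may be included if they have Gleason 6 or 7, (Gleason 3+3 or 3+4), organ confined disease"; the synopsis sets the same limit. Biopsies are scheduled before study entry and at 12 months (section 5.5).

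Section 1.5 says that the numbers for a definitive trial are to be informed by the histological or biological progression rate. Sections 3.4 and 5.6 refer to the section 1.1 definition where continuing on the study is decided.

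**The concern.** The row for 3+3 is open at the top, because it counts score 7 and anything above it. The row for 3+4 is not: it names 4+3 and nothing else. The third row would cover higher scores, but only for a man who starts at 4+3, and such a man is not eligible.

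If the list is coded as written, a 3+4 man who moves to 4+3 is a grade progressor and one who moves to 4+4 or 4+5 is not. The events lost would be the most serious upgrades, and all would come from the higher-grade entry group. Histological progression is reported as a secondary endpoint in its own right, and the progression rate is meant to inform the definitive trial. A downward bias there would carry forward.

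**Working it through.** The protocol gives no figure to reproduce here, so the check is a logical one.

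**Inputs.** Eligible baseline grades are 3+3 and 3+4 (synopsis and section 3.2). The rule is the three rows in section 8.2, read literally and leaving MCCL aside. Follow-up patterns are all nine combinations of primary and secondary grade 3 to 5.

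**Applying the rule.**

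| Baseline | Possible upgrades | Counted by the literal list | Missed |
|---|---|---|---|
| 3+3 | 8 (every pattern except 3+3) | 8 | none |
| 3+4 | 7 (every pattern except 3+3 and 3+4) | 1 (4+3) | 6: 3+5, 4+4, 5+3 (score 8); 4+5, 5+4 (score 9); 5+5 (score 10) |

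The 4+3 row applies to 0 of the 2 eligible baseline grades. If the 3+4 row is extended to 4+3 or any higher score, all 7 upgrades from 3+4 count, and nothing changes for 3+3.

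**Can the lead words serve as the rule instead?** They speak of an increase in Gleason score. A move from 3+4 to 4+3 is listed as progression, yet the sum stays at 7. The lead words alone would therefore exclude an event that the list includes, so the list has to be the operative rule.

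**How many men?** The count is 102 × s × u × (1 − m). Here s is the share entering at 3+4, u the proportion of those upgraded to score 8 or more, and m the proportion of the upgraded men who also have a 50% MCCL rise. The protocol gives none of the three. Purely as an illustration, assume s of 20–40%, u of 3–8%, m = 0 and a repeat biopsy in every man:

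- low: 102 × 0.20 × 0.03 = 0.6 men
- high: 102 × 0.40 × 0.08 = 3.3 men

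For given s and u these are ceilings. Any MCCL overlap lowers them, and so does any omitted biopsy, which section 5.4 allows.

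**The case against.** The strongest reply is that the intent is plain. A move from 3+4 to 4+4 is an increase in Gleason score, and the rows can be read as a ladder on which a man going from 3+4 to 8 has climbed both upper rungs. That is probably what was meant. It stands as a reason not to say that the protocol intends to exclude such men. It does not remove the gap: each row is written from a starting grade, nothing tells the analyst to chain rows, and two programmers could code the list differently. Likewise, the 4+3 row would have a use if an on-study biopsy became the new reference, but the protocol does not say so.

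A second reply is that little depends on it. The primary endpoint is recruitment, the sample size does not use progression, and copies of all pathology reports are obtained (section 5.7), so grades should be recoverable and recoded before analysis. This is right and limits the weight of the point. An analysis plan, not shown here, might also settle the coding. The protocol nevertheless states the definition three times, each time incompletely.

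Two stronger readings are tempting and not supported:

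- A reader might set the upper figure of 3.3 men against 30% of 102 (about 31 men) and infer that a tenth of events are lost. That uses the top of two assumed ranges and makes no deduction for MCCL. It also borrows a denominator from section 3.4, where up to 30% refers to progression at reclassification by MRI and biopsy, not to histological progression alone.
- A reader might infer that a man missed by the grade row is treated as progression-free at 12 months. Section 1.1 is met by any one of several criteria (MRI, PSA, grade, MCCL, metastases), and section 3.4 leaves radical therapy to clinician and patient. No part of the protocol makes management depend on the grade row alone.

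**Conclusion.** The definition is incomplete as written. Taken literally, it counts 4+3 but not score 8 or more as grade progression from 3+4, and it carries a starting row that no eligible baseline grade can meet. This rests only on the protocol's own list and entry criteria, and on baseline being the reference for the comparison.

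The size is unknown and probably small. The illustrative 0.6 to 3.3 men depends wholly on assumed shares. Any bias in the histological progression rate would be downward, through loss of the most serious upgrades. It is a drafting gap worth correcting because the rate is meant to inform the definitive trial, not because it threatens this study's primary result.

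**What to change.** In the analysis definitions in sections 2.2 and 8.2, have the second row read: Gleason 3+4 to 4+3 or any higher Gleason score. Drop the 4+3 starting row, or state that it applies only if an on-study biopsy becomes the reference. Use identical text in both places.

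Section 1.1 needs separate handling, because sections 3.4 and 5.6 cite it where continuing on the study and its medication is decided. The sponsor should reconcile that list with the corrected endpoint definition; no wording is proposed for it here.

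The cost is one line in two sections and a consistency check on a third. It needs no new data, procedures or patients.
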